6.4.3 Pregnancy test

Results of the pregnancy tests (urine or serum) will be listed only.

6.4.4 Vital Signs

Vital signs (diastolic and systolic blood pressure, respiratory rate and heart rate) and their corresponding changes from baseline will be summarized by visit. In addition, at Day 0, pre-dose, 2 and 4 hours assessment will be evaluated. Body surface area measured at Screening will be listed only. The analysis of height, weight and BMI will be described in section 6.4.7.

Vital signs data will be presented overall (all ages) and by age group.

In addition a frequency table of systolic blood pressure for each visit compared to the age, sex, height - adapted SBP median by age group and concomitant PAH medications will be presented. The adapted SBP median is based on the age at visit and actual height at the respective visit, derived from Table 4-1 and Table 4-2 in the study protocol. For Japanese and Taiwanese the 5th and 95th height percentile are not defined and therefore 3rd and 97th height percentile will be used instead, respectively.

Vital signs data are part of the DMC package.

6.4.5 Electrocardiogram (ECG)

ECG will be summarized by visit. In addition, at Day 0, pre-dose, 2 and 4 hours assessment will be evaluated. Investigator assessment and other parameters, including changes from baseline, will be tabulated.

Data will be presented overall (all ages), by age group and concomitant PAH medications. Refer to table shells for more information about the subgroup presentation.

ECG outputs are part of the DMC package.

6.4.6 Left hand X-ray

Bone age and bone morphology will be evaluated centrally by external X-ray specialist based on left hand X-ray at Day 0, week 24 and every 12 months during the LTE until growth velocity is plateauing and growth plates are closed. Data will be summarized by visit and will be presented overall (all ages).

Left hand X-ray outputs are part of the DMC package.

6.4.7 Physical examination and growth chart

Subject's overall development is assessed by physical examination, growth chart (height and weight) evaluation and pubertal development using Tanner scale, see protocol section 18.3, and at the discretion of the investigator in case of clinical suspicion for bone and/or growth anomalies. Pubertal assessment using Tanner scale will be performed every 12 months. Abnormal physical examination findings are recorded as medical history, if they started before providing written informed consent/assent. If the abnormal finding started or deteriorated after providing written informed consent/assent, it is documented as adverse event.

Height, weight, BMI will be summarized by visit and will be presented overall (all ages), excluding subjects with down-syndrome. BMI will be presented for non-Asian, i.e. excluding Japanese and Taiwanese, population only.

In addition a frequency table of growth parameter percentiles by visit and by age group and concomitant PAH medications will be presented for height, weight and BMI. Subjects with down-syndrome will be excluded. The percentiles are based on CDC growth standards [6] and growth chart for Japan for Japanese and Taiwanese subjects provided by sponsor [7].

For the calculation of percentiles, age in months at each visit will be calculated. Due to the fact, that only year of birth is collected the calculation of age in months will be:

$(\text{year of visit} - \text{year of birth}) * 12$

Pubertal assessment using Tanner scale will be summarized as shift table for change from baseline by visit.

Growth parameters by visit and Tanner scale listing are part of the DMC review.

7. Document history and changes in the planned statistical analysis

- SAP final version 1.0, dated 12 OCT 2015
- SAP final version 2.0, dated 15 JAN 2016. SAP was updated to reflect protocol changes and is based on protocol version 2, Amendment 3, from 24 NOV 2015.
- SAP final version 3.0, dated 24 AUG 2016. SAP was updated to reflect protocol changes and is based on protocol version 3, Global Amendment 5, from 31 MAY 2016 and stand-alone Amendment 4, from 08 MAR 2016. Further updates were done to reflect the changes of the DMC Charter and is based on the DMC Charter version 3.0, from 01 JUN 2016.

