### 7.2 Analysis sets

Safety analysis set (full analysis set, FAS): this population will include all subjects assigned to receive study medication who received at least one dose of study medication.

Listing only set (LOS): this population includes all screening failures.

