#### 7.4.1 Safety analysis - amended

The primary objective is to evaluate the safety and tolerability of riociguat in children with PAH. Primary endpoint of the study is: Change from baseline to end of treatment (week 24) of safety and tolerability assessed by incidence of adverse events and serious adverse events, recording of vital signs and left-hand X-ray and laboratory panel.

The safety evaluation of adverse event (AE) data will include:

- The incidence of treatment-emergent AEs (TEAEs). Adverse events are considered to be treatment-emergent if they have started or worsened after first application of study drug up to 2 days after end of treatment with study drug.
- Tables of serious and/or drug-related treatment-emergent AEs, treatment-emergent AEs leading to discontinuation of study drug and AEs of special safety interest.

- The incidence of AEs during pre-treatment and during follow-up (i.e. AEs occurring more than 2 days after end of treatment with study drug).
- Listings of serious adverse events (SAEs), AEs leading to discontinuation of study drug and AEs of special safety interest.
- Descriptive summaries of mortality in the study.
- Listing of deaths in the study period, including day of death relative to start and stop of study drug and cause of death.

The safety evaluation of laboratory data will include:

- Incidence rates of treatment-emergent laboratory values outside of normal range
- Incidence rates of pre-specified laboratory data abnormalities
- Descriptive analysis of laboratory parameters (AST, ALT, BUN, creatinine, GGT, UA, T-Bil, Alb, Na, K, Ca, P, and CBC) and their corresponding changes from baseline

Other evaluations of safety data will include:

- Descriptive analysis of body weight, vital signs, ECG parameters, left hand x-ray and their corresponding changes from baseline.
- Tabulation of ECG status pre-dose, 2 and 4 hours post treatment-initiation.
- Incidence rates of treatment-emergent ECG abnormalities.

Time points of assessment: Assessment of adverse events at baseline, at all visits in the titration phase and maintenance phase, and every 3-4 months in the extension phase. Left hand x-ray at baseline, end of study treatment period (week 24) and every 12 months until growth plates are closed.

For details on safety variables, see section 6.2.

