2 TO 18 YEARS**

NAME \_\_\_\_\_

[figure not shown]
RECORD # \_\_\_\_\_

**GIRLS WITH DOWN SYNDROME  
PHYSICAL GROWTH:  

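### The SAP drops treated children with Down syndrome from its only by-visit height and weight summary; for body weight this departs from the protocol's safety analysis in all treated children

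*SAP*

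**What the plan says.** SAP 6.4.7 describes two growth outputs, each with its own exclusion.

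- By-visit summary: "Height, weight, BMI will be summarized by visit and will be presented overall (all ages), excluding subjects with down-syndrome".
- Frequency table of growth percentiles: "Subjects with down-syndrome will be excluded". Its references are the CDC standards, and a Japanese chart for Japanese and Taiwanese children. No Down syndrome reference is named.

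SAP 6.4.4 (Vital Signs) defers to that section: "The analysis of height, weight and BMI will be described in section 6.4.7". SAP 6.4 lists body weight among the safety assessments and states that safety tables are for the safety analysis set (SAF).

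Protocol 7.4.1 plans a "Descriptive analysis of body weight, vital signs, ECG parameters, left hand x-ray and their corresponding changes from baseline". The only analysed set in Protocol 7.2 is the safety set: "this population will include all subjects assigned to receive study medication who received at least one dose of study medication". SAP 5.1 repeats that definition. Protocol Appendix 1 (18.1) includes growth charts for boys and girls with Down syndrome; one is headed "GIRLS WITH DOWN SYNDROME".

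**The concern.** Leaving these children out of CDC or Japanese percentiles is reasonable, because those references may not describe their growth. The same reason does not reach the by-visit summary. A weight in kilograms, a height in centimetres and the change from a child's own baseline can be summarised without any reference population.

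Growth is not a side issue in this trial. Protocol 1.2 reports bone changes in growing rats, Protocol 8.8 makes bone and/or growth anomalies an adverse event of special interest, and Protocol 6.2 places growth chart evaluation under bone monitoring that the DMC reviews. If treated children are filtered out, the height and weight summary no longer describes the treated population. It may also not match the bone age table beside it.

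**Working it through.** There is no plan figure to reproduce, so the check is mainly a comparison of texts.

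**1. Is the exclusion confined to percentiles?** No. It appears once for the by-visit summary and again, separately, for the percentile table.

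**2. Is weight by visit summarised elsewhere without the exclusion?** None is specified. SAP 6.4.4 sends height, weight and BMI to 6.4.7. SAP 6.1.3 covers demographic data at screening and does not name weight.

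**3. Does the protocol allow the exclusion?**

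| Source | Measure | Population |
|---|---|---|
| Protocol 7.4.1 with 7.2 | Body weight and change from baseline | All treated |
| SAP 6.4 with 5.1 | Safety data, body weight named | SAF, i.e. all treated |
| SAP 6.4.7, by-visit summary | Height, weight, BMI | Treated children without Down syndrome |

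The protocol conflict is explicit for body weight. Protocol 7.4.1 does not name height or BMI; for those the conflict is with the SAP's own SAF rule.

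**4. Do neighbouring outputs exclude these children?** SAP 6.4.6 (bone age and morphology) states no such exclusion, nor does the Tanner shift table in 6.4.7. The blood pressure table in 6.4.4 also states none, although its reference level depends on height percentile.

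**5. Is the departure recorded?** Protocol 7.1 says that revisions will be identified in the final SAP. SAP section 7 lists what changed in each version and does not mention this exclusion. SAP 6.4.7 gives no reason for it.

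**6. Could such children be enrolled?** Down syndrome is not named among the exclusion criteria in Protocol 4.3, and Appendix 1 supplies charts for it. They were anticipated.

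**7. Size.** The documents do not give the number k of treated children with Down syndrome. Protocol 4.1 and 7.5 give a minimum of 20 children on an ERA; I take 20 as the number treated. The by-visit summary is presented overall, so the share removed is k/20:

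- k = 0: 0/20 = 0%, and the exclusion has no effect
- k = 1: 1/20 = 5%, leaving 19
- k = 2: 2/20 = 10%, leaving 18
- k = 3: 3/20 = 15%, leaving 17
- k = 4: 4/20 = 20%, leaving 16

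If each child has Down syndrome independently with probability p (also an assumption), the chance that at least one of 20 is removed is 1 − (1 − p)^20. This gives 0.33 for p = 2%, 0.64 for 5%, 0.88 for 10% and 0.99 for 20%. The documents do not favour any of these values.

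**The case against.** The best defence is that little is lost. SAP 6.4 also presents safety data in listings, and the exclusion is not stated for those. Bone age and morphology, which belong to the primary safety outcome, cover these children and go to the DMC. So do skeletal events of special interest. The Tanner shift table covers them too, and abnormal physical findings that start or worsen after consent become adverse events. The study is descriptive, and no decision rule rests on mean height or weight. Protocol 7.1 leaves detail to the SAP.

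Most of that stands, and it rules out several stronger readings that a reader might infer.

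- *These children vanish from growth safety monitoring.* They do not; they leave the height and weight summaries. Even the DMC effect is uncertain. The SAP says that growth parameters by visit and Tanner scale listing go to the DMC, and the word listing may cover both.
- *The protocol is contradicted for height and BMI.* It is not; 7.4.1 names body weight only.
- *Affected children are likely because repaired congenital heart disease is eligible.* The documents state no link with Down syndrome and no frequency. The charts show anticipation, not likelihood.
- *The supplied charts make full Down syndrome percentiles straightforward.* The use that Protocol 5.1.1 states for the Appendix 1 charts is the height percentile for the blood pressure reference. Amendment 3 mentions height and weight scales but no BMI. Age at visit is derived from year of birth alone, so percentiles read from the charts could be displaced by months.

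What the defence does not supply is a reason to remove treated children from a raw weight summary, or to leave the departure unrecorded.

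**Conclusion.** The point holds in a narrow form. The SAP removes treated children with Down syndrome from the only by-visit height, weight and BMI summary that it specifies. For body weight this departs from Protocol 7.4.1 read with 7.2; for all three measures it departs from SAP 6.4. The departure is unexplained and is not in the change history. The percentile exclusion is not at fault.

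The size is unknown and may be nil: 5% to 20% of 20 treated children if 1 to 4 have Down syndrome, and a smaller share for the same number if more than 20 are treated. The conclusion on the text does not depend on that assumption. The words "all treated" come from reading 7.4.1 together with the protocol's single safety set, since no exclusion for Down syndrome appears in its analysis sections. This is a minor correction, worth making because it is nearly free and restores a safety summary that the protocol specifies.

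**What to change.** In SAP 6.4.7:

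1. Remove the Down syndrome exclusion from the by-visit summary, so that raw height and weight, with changes from baseline, are summarised in the full SAF.
2. Keep the exclusion for the CDC/Japanese percentile table, and state the reason.
3. Record any exclusion that remains, with its reason, in SAP section 7.
4. Say whether the DMC growth output is a table or a listing. If it is a table, give it the same population as item 1.

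Listing height and weight percentiles from the Down syndrome charts in Protocol Appendix 1 is optional; BMI should not be promised from them.

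The cost is one filter removed from one set of tables and a few sentences in the SAP. No new data are needed.

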## 5. Treatment groups and regimens

### 5.1 Method of treatment allocation

Allocation to treatment dose will be done centrally by an interactive voice / web response system (IxRS). All subjects will be allocated to riociguat body-weight adjusted, individual dose titration (IDT).

The investigator will provide the IxRS with study center identification, the subject's date of birth (year) and age, gender, and weight. Further details are contained in the IxRS manual.

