## 8.8 Adverse events of special interest

The following AEs are of special interest:

- Symptomatic hypotension
- Hemoptysis
- Bone and/or growth anomalies

Symptomatic hypotension, hemoptysis as well as bone and/or growth anomalies have been defined as adverse events of special interest and must be documented accordingly in the corresponding adverse events of special safety interest pages in the electronic case report form (eCRF). Events of special interest should not automatically be upgraded by the reporting Investigator to serious. Declaration of an event as serious should only occur when one or more of the serious criterion (as defined in Section 8.1.2) is applicable.

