6.1.3 Demography

Demographic data includes age at screening (years), sex, race and smoking among others. This data will be listed and summarized in tables. Summaries will be presented overall (all ages), by age group and concomitant PAH medications for SAF set and will be repeated for subjects who discontinued treatment.

The above presentation will be part of the DMC package.

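### The growth-percentile table derives age from calendar years alone, so every child ages either 0 or 12 months between baseline and week 24 instead of about 5.5

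*SAP*

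**What the plan says.** SAP 6.4.7 plans a "frequency table of growth parameter percentiles by visit and by age group and concomitant PAH medications will be presented for height, weight and BMI". Children with Down syndrome are excluded. The reference is the CDC growth standard, or a Japanese chart for Japanese and Taiwanese children. "For the calculation of percentiles, age in months at each visit will be calculated", and the rule is introduced with "Due to the fact, that only year of birth is collected the calculation of age in months will be". The formula that follows takes the year of the visit, subtracts the year of birth and multiplies by 12. The month and day of the visit do not enter.

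Other places bear on what is known about age. Protocol 5.1 has the site give the allocation system the "date of birth (year) and age, gender, and weight". SAP 6.1.3 states: "Demographic data includes age at screening (years), sex, race and smoking among others". The notes to Protocol Tables 4–1 and 4–2 round age at the half-year, so sites know it more finely than whole years. No other section adds visit month, a mid-year birth date or screening age to the growth derivation.

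Protocol 8.8 states that "bone and/or growth anomalies have been defined as adverse events of special interest". SAP 6.4.7 sends growth parameters by visit to the DMC, without saying whether that includes the percentile table.

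**The concern.** A growth percentile compares a child with others of the same age, so it is only as good as the age supplied. Under this rule age stands still within a calendar year and jumps 12 months on 1 January. While reference height or weight is still rising, a child whose visits all fall in one year drifts upward in percentile. A child whose visits straddle the new year appears to drop. Height and weight are taken at every visit, so a child seen in late December and again two weeks later ages a full year in between.

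This is the only growth output in SAP 6.4.7 that sets each child against an age reference, in a trial where growth anomalies are of special interest. The protocol plans at least 20 ERA-treated children and as few as 5 in an age cohort. The table is split by age cohort and by PAH medication, so even one misplaced child can alter a cell.

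**Working it through.** **Inputs.** The formula is from SAP 6.4.7. Follow-up is 24 weeks = 168 days, with ±5 days at Visit 9 (protocol flow chart). Even spread of visit and birth dates over the year is an assumption of this check. The documents give no figure of their own to reproduce.

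**Change in age, Visit 1 to Visit 9**

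- True change: 168 / 30.4375 = 5.52 months (5.36 to 5.68 over the ±5-day window).
- Derived change: 12 × (year of V9 − year of V1). Birth year cancels, so the only possible values are 0 and 12.
- The switch comes when Visit 1 falls on or after about 17 July.
- Error per child: 0 − 5.52 = −5.52, or 12 − 5.52 = +6.48 months.
- Share with a 12-month step under even entry: 168 / 365.25 = 0.460 (0.446 to 0.474 over the window). Share with 0: 0.540.
- Among 20 children: 20 × 0.460 = 9.2 with a 12-month step; the binomial 95% range is 5 to 14.
- Mean error: 12 × 0.460 − 5.52 = 0. SD: 12 × √(0.460 × 0.540) = 5.98 months. SE of the mean: 5.98/√20 = 1.34 months for 20 children and 5.98/√5 = 2.7 for 5.
- In a cohort of 5, the chance that at least 4 share the same wrong step is 38% (binomial, p = 0.46).

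Two examples, birth year 2008:

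| Visit 1 | Visit 9 | Derived age (months) |
|---|---|---|
| 1 Mar 2018 | 16 Aug 2018 | 120, then 120 |
| 1 Sep 2018 | 16 Feb 2019 | 120, then 132 |

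**Age at a single visit.** The error is the position of the birthday in the year minus the position of the visit in the year. With both uniform:

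- mean 0; SD √2 × 12/√12 = 4.90 months
- mean absolute error 12/3 = 4 months
- share above 6 months (6/12)² = 25%
- maximum just under 12 months

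**What this could do to a height percentile (illustration).** Assumed figures not in the documents: reference growth 0 to 7 cm/yr and height SD 5.5 to 7.5 cm. It also assumes that the derived age is correct at baseline. The apparent shift in z is growth × 5.52/12/SD upward or growth × 6.48/12/SD downward.

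| True percentile at both visits | Growth | Week 24, 0-month step | Week 24, 12-month step |
|---|---|---|---|
| 50th | 0 cm/yr | 50th | 50th |
| 50th | 3 cm/yr | 57th–60th | 38th–41st |
| 50th | 7 cm/yr | 67th–72nd | 25th–31st |
| 5th | 5 cm/yr | 9th–11th | 2nd |

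On average the error is split between the two visits. Children with a 12-month step average about −3.2 months at Visit 1 and +3.2 at week 24; those with a 0 step average +2.8, then −2.8. The size of the apparent shift in z stands, but the displacement from truth at week 24 alone is on average about half of that shown.

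**The case against.** The case for leaving this alone has several parts.

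- **The table is cross-sectional.** SAP 6.4.7 plans percentile counts at each visit; only Tanner stage gets a shift table. The 0-or-12 step is therefore never tabulated as a within-child change. This is true, but a by-visit table is read across visits, and the single-visit error misplaces children in its own right.
- **The fix removes only part of the single-visit error.** This stands: the SD falls from 4.9 to 3.5 months, about 30%. What the fix removes entirely is the error in change.
- **The error averages to zero.** Only with evenly spread entry and enough children. Entry is staged by age cohort, cells are small, and a frequency table counts individuals, so a misplaced child stays misplaced.
- **Category changes cannot be counted.** This stands. The growth-chart values and category limits are not in the text, so the percentile illustration is only that.
- **Safety does not rest on this table.** This also stands. Events of special interest are reported by investigators. Site growth charts, examination, Tanner stage, central bone age and raw height, weight and BMI do not use the formula. The analysis is single-arm and descriptive, with no decision rule on these percentiles.

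These points limit the weight of the concern. None of them makes the formula right.

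**Conclusion.** The concern holds and should be fixed. The rule gives wrong ages as written: every child's ageing from Visit 1 to week 24 is off by −5.5 or +6.5 months, whatever the birth date. That result needs no assumption beyond the formula and the 24-week schedule. The 54%/46% split, the 9 of 20 and the single-visit SD of 4.9 months rest on evenly spread dates. The stated reason does not justify the rule, because visit dates are already held.

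The consequence is modest: a supportive table that can mislead about growth, not a loss of safety monitoring. Scope may be wider than this table. SAP 6.4.4 compares SBP at each visit with a median based on age at visit and height, using protocol tables indexed by height percentile, and gives no separate rule for that age. If it uses the same derivation, it is affected too.

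**What to change.** In SAP 6.4.7, impute one birth date per child and use the actual visit date: age in months = (visit date − 1 July of the birth year) / 30.4375. Change between visits is then exact. The remaining error is constant within a child, at most about 6 months, with SD 12/√12 = 3.5.

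If age at screening reaches the analysis data independently of birth year, use instead the midpoint of the birth dates compatible with birth year, completed age and screening date. The SD is then about 2.4 months. If screening age is itself derived from birth year, this adds nothing and the 1 July rule should be used.

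State in SAP 6.4.4 which age at visit feeds the SBP comparison, and align it if it uses the calendar-year rule.

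The cost is one changed derivation in the SAP and in programming, plus that check. No new data are needed.
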